## APPLICATION & PROTOCOL

7d	Does the participant or family member have the option not to know the results? If yes, how will this decision be recorded:			
	 Subjects will not be contacted in the future as there will be no relevant genetic clinical data to share. The subject can indicate on the consent form whether or not s/he agrees to have a small number of genes (maximum 7) known to be involved in metabolism and excretion of BaP analyzed. The results will not be shared as there is no established disease risk.			
7e	Could other clinically relevant information be uncovered by the study? If yes, explain how (or if) disclosure of this information will occur:			
				
7f	Do any practical limitations exist on the participant's right to withdraw from the research, withdraw data, and/or withdraw DNA? If yes, explain:			
				
7g	Is the participant permitted to participate in the study if they decline to participate in the genetic testing?			
8	Will samples be stored for future studies?			Skip to 8e
8a	Indicate how long samples will be retained, how they will be stored, and what they will be used for:			
	 Samples and data will be identified only by an anonymous code. After analysis for this study, the coded samples will be stored in LPSC 389 at OSU indefinitely unless not allowed by subjects. Data will be stored securely on password protected computers or in locked file cabinets in LPI. If subjects decline permission to store samples beyond the scope of this study, their samples will be properly discarded after analysis. Samples and data will only be used in future PAH-related studies.			
8b	The information in the consent form should convey the disease, condition, or specific field of study for future projects. Explain whether and how participant permission will be sought for future studies of existing samples:			
	 As stated in the consent form, we will not contact subjects for permission to use their samples and data in future projects. The consent form includes a section for subjects to give permission to use their samples and data in future projects without being contacted for consent. They may withdraw permission at any point during the study.			
8c	Indicate whether participants will be contacted by researchers in the future for the purpose of updating information:			

# APPLICATION & PROTOCOL

	No			
8d	Indicate whether and how participants can opt out of any sharing or future use of their sample:			
	The consent form includes a section for subjects to give permission to use their samples and data in future projects without being contacted for consent. They may change their answer at any point during the study. Since the AMS analysis at LLNL is the primary method of analysis for this study, subjects will not be offered the option to opt out of sharing their sample with LLNL.			
	The Biological Safety Officer will review this portion of the submission unless the materials are exempt from biosafety review			
8e	Provide location(s) of material handling, manipulation, and storage at OSU (i.e., building and room):			
	Samples will be collected in LPSC 407. Processing and storage will take place in LPSC 389.			
8f	Provide the names of all personnel who will be working with biological materials:			
	[name] and [name]			
	All personnel who will be working with biological materials must have current Blood-borne Pathogens Training and any required vaccinations. Information about current status accessed from the EH&S website			
SECTION 30 - Privacy and Confidentiality			Yes	No
	Many of the terms used in this section are defined in the glossary under the heading "Privacy, Confidentiality, and Identifiers".			
1	Privacy, in the context of a research protocol, means respecting an individual's right to be free from unauthorized or unreasonable intrusion, including control over the extent, timing, and circumstances of obtaining personal information from or about them. Explain how privacy will be respected when identifying and recruiting potential participants:			
	With the exception of contacting individuals on the LIFE registry maintained by the Center for Healthy Aging Research (CHAR) at OSU, only subjects requesting information about the study will be contacted, and no subjects will be prospectively contacted by researchers without contact first being initiated by the individual. We will protect email correspondence by deleting after the subject has completed the study, is removed, withdraws from the study, or has been found to not qualify. Telephone and in-person screenings will take place in a private location with time between subject visits to maintain privacy.			

# APPLICATION & PROTOCOL

	We will immediately destroy notes taken during telephone screening conversations with excluded subjects. We will securely retain records from subjects who are excluded from the study after being enrolled.			
2	Will direct and/or indirect identifiers be requested or recorded?			
3	If no, will all data be collected anonymously or provided to researchers without identifiers?			Skip to section 31
4	List the direct identifiers (e.g., names, social security numbers, addresses, telephone numbers, student ID, medical record number, mTurk ID, photographs, video recording):			
	Name, address, email address, telephone number, date of birth			
5	Indicate whether identifiers or codes will be retained that could link the identity of the participant to the sample:			
	Samples will be labeled only with codes. Only study team members will have access to study samples. If a student employee is hired to assist with processing of de-identified study samples, s/he will always be supervised by [name], [name] or [name].			
6	List the indirect identifiers (e.g., combination of demographic and other variables such as gender, race, ethnicity, age, zip code, company affiliation, class standing, department, audio recording):			
	Age, gender, race, ethnicity – this data will be collected on forms containing only subject codes, not direct identifiers			
7	Describe the steps that will be taken to minimize the chances of a breach of confidentiality during and after data collection (e.g., coding system, pseudonyms, etc.)			
	Only the nurse coordinator will have access to the document linking identifiers to subject code numbers. Personal information collected during telephone screening, the consent documents, and compensation acknowledgement form will be the only documents containing direct identifiers. We will store this information separately from coded data. These documents will be stored in a locked file cabinet in a secure office. Direct identifiers will be stored in hard-copy only.			
	Details of data security will be collected in later section.			
8	Will a copy of the consent form, test results, or other research study information be placed in the participants' record (e.g., medical, personnel, or education record)?			
SECTION 31 - Record Retention			Yes	No
1	Will the Principal Investigator store research records in a secure and audit accessible manner for a			

## APPLICATION & PROTOCOL

	minimum of three years post-study termination?			
2	If not, provide justification for early destruction:			
				
3	Will the student researcher also store research records after the study has closed?			
3a	Will the records stored by the student contain individually identifiable information?			
4	If the study is FDA-regulated, confirm the PI will also comply with the following relevant records retention requirements:			
4a	In accordance with 21 CFR 312 (drugs) , an investigator or sponsor shall retain the records and reports for 2 years after a marketing application is approved for the drug; or, if an application is not approved for the drug, until 2 years after shipment and delivery of the drug for investigational use is discontinued and FDA has been so notified.			
4b	In accordance with 21 CFR 812 (devices) , an investigator or sponsor shall maintain the records required by this subpart during the investigation and for a period of 2 years after the latter of the following two dates: The date on which the investigation is terminated or completed, or the date that the records are no longer required for purposes of supporting a premarket approval application or a notice of completion of a product development protocol.			
5	Will a link between study code numbers and direct identifiers be retained after data collection is complete?			
6	If yes, explain why this is necessary and state how long the link will be retained:			
				
7	If audio and/or video recording, indicate whether these files will be destroyed after transcripts and/or coding is verified. If A/V files will be retained, provide justification for retention:			
				
8	Will data be stored for future studies?			Skip to next section
8a	Indicate how long data will be retained, how it will be stored, and what it will be used for:			
	See section 29			
8b	The information in the consent form should convey the area of study for future projects. Explain whether and how participant permission will be sought for future studies of existing data:			

# APPLICATION & PROTOCOL

					
8c	Indicate whether participants will be contacted by researchers in the future for the purpose of updating information:				
					
8d	Indicate whether and how participants can opt out of any sharing or future use of their data:				
					
SECTION 32 – Sharing Data and Biological Samples			Yes	No	N/A
1	Will data and/or samples be shared with individuals or entities external to OSU (e.g., made public, shared with sponsor, sent to collaborators, given to people at the site of research, etc.)?				
1a	Why and with whom?				
	A portion of the de-identified coded study samples will be forwarded to LLNL for analysis with no personal identifying information contained within the shipment, so there is no risk of loss of confidentiality with the mailing of samples nor the analysis of samples at LLNL. Data returned to OSU will be identified only by de-identified codes, so there is no risk of loss of confidentiality.				
1b	Will shared data and/or samples be individually identifiable?				
1c	Will data security plan at the external site match or exceed the OSU data security plan?				
1d	If the data security plan at the external site will not match or exceed the OSU data security plan, explain:				
					
1e	Describe how security will be maintained in transit:				
	A portion of the de-identified coded study samples will be forwarded to LLNL for analysis with no personal identifying information contained within the shipment, so there is no risk of loss of confidentiality with the mailing of samples nor the analysis of samples at LLNL. Data returned to OSU will be identified only by de-identified codes, so there is no risk of loss of confidentiality.				
2	If the study is federally funded, provide the plan to comply with federal data sharing requirements:				
	Oregon State University adheres to the NIH Grants Policy Statement on Availability of Research Results: Publications, Intellectual Property Rights, and Sharing Research Resources as described in https://grants.nih.gov/grants/policy/nihgps_2013/nihgps_ch8.htm#_Toc271264947 . Specifically, material transfers would be made with no more restrictive terms than in the Simple Letter Agreement or the UBMTA and without reach through requirements. Should any intellectual property arise which requires a				

## APPLICATION & PROTOCOL

patent, we would ensure that the technology remains widely available to the research community in accordance with the NIH Principles and Guidelines document. We do not anticipate generating and unique genetic animal or biological reagents (e.g., plasmids). All publications and presentations of results will be made available to interested researchers. The centralized data management organization facilitating the publication of data to the NIEHS Chemical Effects in Biological Systems Knowledge Base for public availability of Program data. The bioinformatics software updates will be released in the Bioinformatics Resource Manager (BRM) software as version 2.2. BRM is a client-server application, and account registration is required to store each user's personal data securely on remote servers. We also want to ensure our AMS data with human carcinogen micro-dosing, is available to EPA as quickly as possible. We intent to provide EPA ORD, NCEA, IRIS with password protected access to de-identified clinical data at the earliest possible time.
				
3	Will the intent to share data be disclosed to research participants as part of the consent process? If not, provide justification:			
 SECTION 33 – Publication		Yes	No	N/A
1	Could participants be identifiable in publication or presentation (e.g., results will be reported using direct quotes, group or tribe name, company name and position title)			
2	Will manuscripts, presentation materials, theses, or dissertations be stored in Scholars Archive?			
3	Will individually identifiable data or specimens be stored in an archive or repository? If yes, describe:			
				

# APPLICATION & PROTOCOL

SECTION 34 - Data Security			Breach of confidentiality poses what level of risk?				
Use this matrix to determine the data security level and related requirements for this study.							
		No Risk	Minimal Risk	Greater than Minimal Risk			
Are data and/or subjects:	De-Identified or anonymous?	Level 1	Level 1	Level 2			
	Identifiable or coded?	Level 1	Level 2	Level 3			
Complete only the subsection for the appropriate level of data security below.							
SECTION 34.1 - Level 1					Yes	No	N/A
1	Will the following security requirements be met: 
 
Information will be shared and stored in a manner that provides access only to authorized individuals.
 
If information is stored on a computer, the system will have fully patched operating systems and applications, and current antivirus software with current virus definitions. Information may be stored in cloud-based servers.
 
						
2	If not, provide justification:						
3	Will the following security recommendation be met: 
 
A plan for routine back-ups of all data will be in place
 
						
4	Outline any additional safeguards that will be taken:						
							
SECTION 34.2 - Level 2					Yes	No	N/A
1	Will the following security requirements be met: 
 
Information will be shared and stored in a manner that provides access only to authorized individuals.
 
Data will not be disclosed to additional parties without prior IRB approval specifically authorizing the
 
						

# APPLICATION & PROTOCOL

	
disclosure.
 
 
• If information is stored on a computer, the system will have fully patched operating systems and applications, and current antivirus software with current virus definitions.
 
• Information may be stored on cloud servers licensed by OSU. A plan for routine back-ups will be in place.
 
• If subjects will be asked to use a third-party website or application, or if a cloud-based server will be used, the researchers will review the data security plan with the Information Security Office before initiating the study. Exceptions include servers and software licensed by OSU.
 
			
2	If not, provide justification:			
3	Will the following security recommendation be met:			
4	Outline any additional safeguards that will be taken:			

 
SECTION 34.3 - Level 3
				
1	
Will the following security requirements be met:
 
 
• Information will be shared and stored in a manner that provides access only to authorized individuals.
 
• Data will not be disclosed to additional parties without prior IRB approval specifically authorizing the disclosure.
 
• If information is stored on a computer, the system will have fully patched operating systems and applications, and current antivirus software with current virus definitions.
 
• When feasible, information will be stored in a local system of record (e.g., local server, approved cloud).
 
• All mobile computer systems or portable storage media will be encrypted with at least the 256-bit encryption common in operating systems and encoding devices sold in the United States.
 
• If the data are coded, and there is a linked list of codes and identifiers, this list will be stored separately from all coded data.
 
• Identifiable information will not be stored on student researchers' computers after the study has ended, unless justified elsewhere in this section and approved by the IRB.
 
• Computers must have host-based firewalls enabled in addition to being behind a networked firewall context.
 
• A plan for routine back-ups of all data must be in place, with the appropriate security mechanisms for
 
			

# APPLICATION & PROTOCOL

	
that data, including encryption and physical security addressed.
 
 
• The researchers will review the data security plan with the Information Security Office before initiating the study.
 
			
2	If not, provide justification:			
				
3	Outline any additional safeguards that will be taken:			
				
	Researchers using cloud-based servers, or third party websites or applications, that are not licensed by OSU, and those collecting level 3 data can minimize delays by consulting with the Information Security Office prior to submitting the application materials to the HRPP for review .			
SECTION 35 - Mandatory Reporting		Yes	No	N/A
	Under Oregon state law, all OSU employees are mandatory reporters.			
	Reporting requirements related to child abuse or neglect.			
	Reporting requirements related to sexual assault or misconduct			
	What is the impact of mandatory reporting legislation on IRB-approved research?			
	What do I do if a research participant tells me about an experience with sexual harassment or sexual violence?			
1	Study includes collection of information regarding child abuse or neglect OR it is reasonable to expect that child abuse or neglect could be observed or revealed to the researchers			
2	Study includes collection of information regarding sexual harassment or sexual violence OR it is reasonable to expect that such information could be revealed to the researchers			
3	Study includes collection of information regarding harm to self or others OR it is reasonable to expect that such information could be observed or revealed to the researchers			
4	Researchers plan to report information regarding harm to self or others and this is disclosed to potential participants as part of the consent process			
5	If yes to any of the above items in this section, describe the relevant training that study team members have, or will receive, to minimize risks to participants and comply with the reporting requirements:			
				

# APPLICATION & PROTOCOL

SECTION 36 - Certificate of Confidentiality		Yes	No	N/A
	Certificate of Confidentiality			
1	A Certificate of Confidentiality has been automatically deemed issued because this study is NIH-funded and includes individually identifiable data			
2	A Certificate of Confidentiality from the NIH has been obtained or will be sought for this study because it includes the collection of individually identifiable, "sensitive" data			
SECTION 37 - Risks		Yes	No	N/A
	Minimal risk means that the probability and magnitude of harm or discomfort anticipated in the research are not greater in and of themselves than those ordinarily encountered in daily life or during the performance of routine physical or psychological examinations or tests.			
	It is not sufficient to describe the risks as "minimal" without identifying what those risks are. Include risks of potential harm that are physical, mental/emotional, legal, financial, insurance, employment, or social and reputational risks.			
	In all cases where participants are known to the investigators, there is the chance of a breach of confidentiality. However, if there is no potential for harm associated with such a breach, it need not be listed in this section. The ways in which the potential for a breach of confidentiality will be minimized should be articulated in the anonymity and confidentiality section.			
	Investigators should consider risks to entire groups under study (e.g., tribes, ethnic or racial groups, economic classes).			
1	Does the study involve greater than minimal risk to adult participants?			
2	If children will be enrolled, which of the following four federal categories applies (check "yes" only once for 2a – 2d):			
2a	Research does not involve greater than minimal risk to children.			
2b	Research involves more than minimal risk to children but the study holds prospect of direct benefit to the participants.			
2c	Research involves more than minimal risk to children and there is no prospect of direct benefit to participants, but the study likely to yield generalizable knowledge about the participants' disorder or condition.			
2d	Research is not otherwise approvable under the federal regulations but the study presents an opportunity to understand, prevent, or alleviate a serious problem affecting the health or welfare of the participants.			
3	Describe all reasonably foreseeable risks to study participants:			

## APPLICATION & PROTOCOL

**BaP:** The International Agency for Research on Cancer (IARC) has determined that BaP is a Class 1 known human carcinogen.

**Radiation:** The total radiation dose of 16.4 nCi for the 3 dose cycles of [C]-benzo[a]pyrene (10.8 nCi if only doing 2 dose cycles) is equivalent to about 60 minutes of natural background radiation. The risk from the ultra-low doses in this study is negligible.

**Blood Sampling:** Risks of blood sampling include pain, bruising, and in rare instances, infection. Some individuals can become lightheaded or nauseated.

 **Blood Loss:** The total amount of blood collected from each subject is 420 mL (120 mL for the [C]-BaP only cycle and 155 each for the Brussels sprouts and DIM cycles) or 310 mL if only doing the Brussels sprouts and DIM cycles. The maximum amount of blood collected in an 8 week period is 310 mL.

**Food allergens:** Foods and beverages provided during this study may contain allergens.

**Foodborne illness:** As with any perishable foods, the Brussels sprouts may spoil if improperly stored or may become contaminated.

**Confidentiality/anonymity:** Loss of confidentiality or anonymity is a potential risk.

4 Describe all steps taken to minimize risks:

 **BaP:** Humans are exposed to PAHs, including BaP, from a number of sources, the highest being occupational and smoking, so we are excluding these populations. In the general population, the greatest BaP exposure is through diet (9.5-43.5 ng/day inhalation; 1 ng/day water; 160-1,600 ng/day diet). The dietary restrictions during this study are intended to offset the total 100 ng BaP consumed in 2 study cycles. This is equivalent to less than or equal to 4 ng/day over the 25 day (minimum) study period. We estimate that following our dietary restrictions will reduce subject daily dietary exposure to BaP by 35-54 ng/day. Therefore, subjects are not exposed to an increased risk of cancer.

**Radiation:** The risk from the ultra-low doses in this study is negligible.

**Blood Sampling:** A qualified research nurse or certified phlebotomist will perform blood draws and carry out all necessary precautions to reduce the risk of injury to subjects. Subjects will be encouraged to hydrate with 1-2 glasses of water before blood draws to minimize risk of syncope or lightheadedness.

**Blood Loss:** While the risk of negative impact due to blood loss is negligible, subjects will be asked to refrain from blood donation one month before the study until one month after completion of the final

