Our hypothesis is that pre-administration of Brussels sprouts or 3,3'-diindolylmethane (DIM) will alter [C]-BaP metabolism and increase the rate of elimination consistent with predictions based on a previously developed Physiologically-Based Pharmacokinetic (PBPK) model for BaP. Briefly, this hypothesis will be tested by dosing individuals with 50 ng [C]-BaP alone and, following a 3-week washout period, ingestion of ½ cup (about 44 g) Brussels sprouts or 300 mg of 3,3'-diindolylmethane (DIM) supplement for 1 week prior to the [C]-BaP micro-dose. The impact of the supplement and the whole food will be assessed with respect to alterations in uptake from the GI tract, metabolism and rate of elimination. To date, our accelerator mass spectrometry (AMS) studies with PAHs have not investigated the impact of diet on [C]-BaP pharmacokinetics. The consumption of cruciferous vegetables will be assessed at the beginning of the study by completion of a dietary questionnaire to examine typical eating patterns in the previous 3 months and by collection and extraction of blood and urine to assay for DIM by LC/ESI-MS/MS-SRM. In addition, for each phase, urine will be assayed for DIM as an estimate of crucifer or DIM supplement intake. [C]-BaP and metabolites will be extracted from plasma and urine (with and without  $\beta$ -glucuronidase/sulfatase) and shipped to Lawrence Livermore National Laboratory (LLNL) for UPLC-AMS analysis. The PK parameters will be assessed at PNNL and the impact of Brussels sprout or DIM consumption on uptake, metabolism and elimination of [C]-BaP determined. In preclinical and clinical studies administration of Brussels sprouts or DIM impacts the activity of the same enzymes responsible for the phase 1 (CYP1A1 and CYP1B1) and phase 2 enzymes (GSTM1, UGT, SULT). Monitoring changes in  $\beta$ -estradiol metabolites will confirm the mechanism of alteration in the metabolic profile of [C]-BaP.

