### Summary of samples collected for Brussels Sprouts and DIM cycles

Time point	Total blood collected (mL)	Urine
-7 days	25	Spot
0 (background)	25	Spot
0.25 – 24 hours	90 (9 x 10 mL)	Total urine (0-48 hours)
48 hours	15	

The total amount of blood collected for the BaP-only cycle is 120 mL. The total amount of blood collected for the Brussels sprouts and DIM cycles is 155 mL per cycle.

Subjects who indicate that they have not consumed the Brussels sprouts or DIM capsules as instructed will be allowed to have up to two lapses with subsequent washout and dietary restriction extension before they will be automatically removed from study participation due to lack of compliance.

There will be at least three weeks' washout period between cycles. Previous multiple micro-dosing of the same individual has shown that after 3 weeks there is no detectable [C] in plasma or urine, validating the choice of 3 weeks as adequate for a "washout period". Extending the washout period will not adversely impact the data collected from the subjects but will minimize the subject's exposure to PAHs.

Subjects who have participated in IRB protocol 8233 (Benzo[a]pyrene Ultralow Dose-Response Study) or IRB protocol 8554 (Ultralow Dose PAH Binary Mixture Study) will participate in only the [C]-BaP plus DIM and [C]-BaP plus Brussels sprout cycles if they have complete the 50 ng [C]-BaP-only cycle within the prior 12 months. There is no set order to the Brussels sprouts or DIM cycles.

Subjects will be asked to defer blood donation for one month before, throughout, and for one month after completion of the study. At any point during the study, subjects will be referred to their physician if the study physician or nurse consider this advisable.

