## APPLICATION & PROTOCOL

3a	Samples are being collected separately from any clinically indicated procedure or another approved study			
3b	Study involves taking additional samples during clinically indicated procedure or another approved study			
3c	Study involves using samples leftover from a clinically indicated procedure or another approved study			
4	If blood samples will be collected, provide the maximum volume to be collected in an 8-week period and the frequency of collection:			
	The maximum amount of blood collected in an 8 week period is 310 mL. The [  C]-BaP only cycle involves 120 mL of blood collection. The amount collect for the Brussels sprouts and DIM cycles are each 155 mL. The total amount of blood collected from each subject is 430 mL (1 cycle at 120 and 2 at 155 mL) or 310 mL if they are only doing Brussels sprouts and DIM cycles (2 x 155 mL/cycle).			
	Guidance on Minimal risk blood draw			
5	Will any clinical lab testing be conducted? If yes, describe the purpose of the tests and whether results will be disclosed to participants and/or their treating physician:			
	We will conduct a urine pregnancy test on female subjects at the screening visit and on day 1 of each cycle to ensure no potential for fetal exposure to [  C]-BaP. A positive test result will exclude subjects from further study participation. Results of these tests will neither be disclosed to subjects nor their physician.			
6	Will the human biological material be tested/collected in a CLIA-certified lab?			
	If yes, attach the CLIA certificate			
	Results from lab tests, including urine pregnancy tests, cannot be disclosed to participants unless the lab conducting the test is CLIA-certified. For more information, please see the OSU Guidance for CLIA Certification: http://research.oregonstate.edu/irb/clia-certification-guidance			
		Yes	No	N/A
7	Will the study involve genetic testing?			

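### The stated maximum of 310 mL of blood in 8 weeks is not assured at the minimum cycle spacing the protocol permits

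*Combined protocol and SAP*

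**What the plan says.** **Blood volumes.** Section 29 item 4 and Section 37 item 3 each state: "The maximum amount of blood collected in an 8 week period is 310 mL". In Section 20 the BaP-only cycle takes 120 mL, and "The total amount of blood collected for the Brussels sprouts and DIM cycles is 155 mL per cycle". That 155 mL includes the 25 mL drawn at Visit 0, seven days before the capsule. For three cycles, Section 29 gives a total of 430 mL. Section 37 item 3 prints 420 mL beside the same components. Participants who do only the sprouts and DIM cycles give 310 mL in all.

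**Spacing.** Section 20 requires: "There will be at least three weeks' washout period between cycles". It does not say whether the pretreatment week lies inside that period, and its use of the word cycle points both ways. The feeding instructions place the week ahead of the cycle, while the sampling tables list the day -7 visit within it. For participants rolling over from the earlier studies, Section 19 counts three weeks between BaP doses.

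**Order.** Section 13 item 1 has the BaP dose alone and then, "following a 3-week washout period, ingestion of" sprouts or DIM for a week, followed by the next dose.

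**Exposure.** Section 37 item 4 says the dietary restrictions are "intended to offset the total 100 ng BaP consumed in 2 study cycles" and continues: "This is equivalent to less than or equal to 4 ng/day over the 25 day (minimum) study period".

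**The concern.** The blood maximum and the 25-day minimum seem to rest on different schedules. The count of 25 days leaves no separate place for a pretreatment week, whereas 310 mL in 8 weeks is what Section 13's order produces. Section 20, which staff would use to book visits, is compatible with either.

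At stake is a safety figure given to the IRB in two places. If the permitted minimum spacing can push a participant past it, the figure is not a maximum. The exposure statement also covers only two doses, although three cycles is the default and two is the exception for roll-over participants.

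**Working it through.** **Inputs.** Cycle length is 48 hours, or 2 days (Section 20). Washout is at least 21 days (Sections 13 and 20). Pretreatment is 7 days, with Visit 0 on day -7 (Section 20). I take the BaP-only cycle first, as Section 13 and the cycle numbering do, and count washout from the 48-hour sample unless stated.

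**Blood by day.**
- BaP-only: 20 + 8 × 10 = 100 mL on the dose day, 10 mL at 24 h, 10 mL at 48 h; total 120 mL.
- Sprouts or DIM: 25 mL at Visit 0, 25 + 8 × 10 = 105 mL on the dose day, 10 mL at 24 h, 15 mL at 48 h; total 155 mL.
- Three cycles: 120 + 155 + 155 = 430 mL. This matches Section 29 and not the 420 mL in Section 37.

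**The plan's 25 days.** Two doses with pretreatment inside the washout: 2 + 21 + 2 = 25 days, and 100/25 = 4.0 ng/day. Both printed figures reproduce.

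**Section 13's order.** 2 + 21 + 7 + 2 = 32 days from first dose to last sample, and 100/32 = 3.1 ng/day. If the washout is counted from the dose, the span is 21 + 7 + 2 = 30 days. Roll-over participants also have a pretreatment week before their first dose. Counted from their first Visit 0, the span is 7 + 32 = 39 days on Section 13's order, or 7 + 25 = 32 days with the second pretreatment week inside the washout.

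**Largest volume in any 56-day window, three cycles** (day 0 is the first dose):

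| Schedule | Dose days | Visit 0 days | Last sample | Maximum in 56 days |
|---|---|---|---|---|
| Section 13's order | 0, 30, 60 | 23, 53 | 62 | 310 mL |
| Pretreatment inside washout | 0, 23, 46 | 16, 39 | 48 | 430 mL |
| Gap of 21 days, then 28 | 0, 23, 53 | 16, 46 | 55 | 430 mL |
| Gap of 28 days, then 21 | 0, 30, 53 | 23, 46 | 55 | 430 mL |

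The gap is from the 48-hour sample to the next BaP dose. In the first row, a window opening on day 0 holds 120 + 155 + 25 = 300 mL, and one opening on day 23 holds 155 + 155 = 310 mL, so the stated maximum is met exactly. In the second row every draw falls by day 48. The excess is 430 - 310 = 120 mL, and 430/310 = 1.39. The last two rows show that lengthening only one interval does not help.

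**Threshold.** With equal gaps, the 310 mL maximum holds from 26 days if 8 weeks means 56 calendar days, and from 27 days if the window runs from day d to day d + 56. A gap of 28 days satisfies both.

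**Two cycles.** BaP-only plus one other: 120 + 155 = 275 mL. Sprouts plus DIM: 155 + 155 = 310 mL. Neither can exceed the stated maximum.

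**Three doses, exposure.** 150/48 = 3.1 ng/day at the shorter spacing; 150/62 = 2.4 ng/day on Section 13's order.

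**The case against.** The best defence is that nothing in the plan instructs anyone to exceed 310 mL. The 25-day figure is a denominator in an exposure argument about two cycles, and two cycles never break the maximum. Reaching 430 mL requires a three-cycle participant, pretreatment inside the washout, near-minimum spacing at both intervals, and staff who overlook a written maximum. Three weeks is a floor, and actual visits may well be further apart. All of that stands, and it limits the point to a possible excess. It does not answer it: a stated maximum should be true at the tightest schedule the document allows, and Section 20 allows this one.

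A reader might infer that 25 days is an arithmetic mistake. The documents do not support that. Section 13 is a brief design summary, Section 20 governs procedure, and on Section 20's wording 25 days is a coherent minimum. The fault is that the sections disagree about where the pretreatment week falls.

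A reader might also infer that BaP exposure is understated. It is not. A short denominator overstates the daily dose, so the 4 ng/day bound holds on every schedule above, with three doses as well as two.

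Finally, 430 mL is below the 550 mL in 8 weeks quoted in Section 10.2. That figure belongs to expedited review, which this study does not claim, so it gives context for the size of the excess but does not replace the maximum that the protocol sets for itself.

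**Conclusion.** The point holds as an internal inconsistency that leaves a twice-stated safety maximum unassured. On Section 13's order the maximum is exactly 310 mL. With pretreatment inside the washout, as Section 37's 25 days implies and Section 20 permits, a three-cycle participant at minimum spacing gives 430 mL in 48 days, 39% above it.

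This rests on washout running from the 48-hour sample and on minimum gaps at both intervals. Counting from dose to dose tightens the shorter schedule further (doses on days 0, 21 and 42) and still gives 430 mL. The documents do not say how many of the 7 planned completers will do three cycles, so the number who could be affected is unknown.

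It would go too far to say that the protocol builds in a breach or that participants would be harmed; the documents show neither. The change is worth making because it is cheap and concerns a figure on which the IRB was asked to rely. The 420 mL total in Section 37 is a plain slip, since its own parts sum to 430 mL.

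**What to change.** **Preferred.** In Section 20, state that the 21-day washout runs from the 48-hour sample to Visit 0, so that at least 28 days pass from that sample to the next BaP dose, at each interval. Then conform Section 37 item 4:
- two doses: at least 32 days from first dose to last sample (3.1 ng/day);
- roll-over participants doing only sprouts and DIM: 39 days from their first Visit 0;
- three doses: 150 ng over at least 62 days (2.4 ng/day).

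The 310 mL maximum then stands as written.

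**Alternative.** If pretreatment inside the washout is intended, say so in Section 20 and keep the 25 days. Restate the 8-week maximum as 430 mL in Sections 29 and 37 and in any consent text that repeats it, and add the three-dose case of 150 ng over at least 48 days (3.1 ng/day). This needs the IRB's agreement to the larger volume.

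**In either case**, correct the three-cycle total in Section 37 item 3 from 420 to 430 mL.

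**Cost.** If Section 13's order was already intended, only wording changes. Otherwise the preferred fix adds up to 7 days per interval: 14 days for three cycles, 7 for a two-cycle roll-over. It adds no visit, sample or dose. Section 20 itself accepts longer gaps: "Extending the washout period will not adversely impact the data collected from the subjects".
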